## Background

Tramadol is a commonly used opioid analgesic for the treatment of moderate to severe acute and chronic pain. It is metabolized in the liver by O- and N-demethylation (phase I) and conjugation (phase II). O-demethylation of tramadol to the active metabolite O-demethyltramadol (ODT) is catalyzed by cytochrome CYP2D6, and N-demethylation to N-demethyltramadol (NDT) occurs via CYP2B6 and CYP3A4. The ODT metabolite of tramadol is an active metabolite that has 200-fold higher affinity for opioid receptors than tramadol itself and is thought to be responsible for the bulk of the analgesic effect of tramadol. CYP2D6 is a non-inducible enzyme, and its gene shows marked polymorphism due to which there are large individual and population differences in metabolism, analgesic action, and side effects of tramadol. Individuals carrying two inactive copies of CYP2D6 are poor metabolizers (PM) of tramadol compared to those carrying two copies of the extensive wild allele (EM). Individuals carrying one or more copies of inactive alleles or alleles of reduced CYP2D6 activity are intermediate metabolizers (IM), and those carrying more than two copies of wild alleles for CYP2D6 are ultrarapid metabolizers (UM). In addition to pharmacogenetics, the functional status of the liver and kidneys plays an important role in the pharmacokinetics of tramadol. Tramadol and the ODT metabolite are excreted by the kidneys, therefore renal failure, which is common in intensive care units (ICU), leads to the accumulation of tramadol and the ODT metabolite in the blood. More than 80% of tramadol is metabolized in the liver. There are known to be significant differences in the pharmacokinetics of tramadol between healthy subjects and patients with hepatic failure. In patients with hepatic failure, tramadol plasma concentrations are higher and the elimination half-life is longer. These changes are primarily due to decreased hepatic elimination. Patients in ICU often have mildly reduced liver function as part of multiorgan failure due to sepsis or Systemic Inflammatory Response Syndrome (SIRS), while major abdominal surgery and anaesthesia reduce liver perfusion and contribute to hypoxic liver damage. Drug distribution changes as a result of decreased protein production and changes in extracellular volume, and the activity and metabolic capacity of liver enzymes decreases resulting in increased concentration and decreased plasma elimination of drugs, which is often very difficult to predict. The CYP2D6 genotype-phenotype has been shown to be relatively effective in clinical practice, but it should be noted that a number of genotype-phenotype discrepancies have been documented, therefore the absorption, distribution, metabolism and excretion of tramadol cannot be determined by a single protein genotype. The expression and activity of CYP2D6 is regulated by a number of physiological, pathological and environmental factors. CYP2D6 expression is susceptible to changes in infection states or systemic inflammatory response associated with elevated cytokine values. Expression of CYP2D mRNA and protein is reduced by proinflammatory cytokines in the liver of mice and rats, while administration of anti-inflammatory cytokines such as IL-10 reduces CYP3A activity. This decrease was not observed for CYP2D. At low CYP2D6 activity or when O-demethylation of tramadol is reduced, tramadol is primarily metabolized by N-demethylation. A study in cancer patients known to have a chronic inflammatory condition accompanied by elevated values of proinflammatory mediators showed that elevated IL-6 values correlated with N-demethylation of tramadol and patient tolerance to the analgesic effect of tramadol. Surgical stress, anaesthesia, starvation, postoperative pain, emergency surgery, and surgery for malignant diseases contribute to the development of a systemic inflammatory response. Hypothermia or hyperthermia, leucocytosis or leukopenia, tachycardia and tachypnoea, are clinical components of SIRS which is often difficult to distinguish clinically from acute inflammation, but in both conditions

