### **Design of a research**

The research will be designed as a prospective observational research. The research will include patients hospitalized at the Department anaesthesiology and intensive care unit (ICU) of the Clinical Hospital Osijek, and after the signed informed consent. Informed consent will be signed by the legal guardian if the patient is unable to do so alone for various reasons.

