### **Objectives**

1. measure the plasma concentrations of tramadol, O-demethyltramadol and N-demethyltramadol in a patient admitted to the intensive care unit (ICU) after major abdominal surgery;
2. examine differences in tramadol, ODT and NDT concentrations with respect to CYP2D6 gene polymorphism;
3. examine the effect of systemic inflammation on the concentrations of tramadol, ODT and NDT in the early postoperative period;
4. examine the analgesic effect of tramadol with respect to systemic inflammation and organic dysfunction.

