After signed informed consent, all patients included in the study will have a blood sample taken for analysis of the CYP2D6 polymorphism, and ultrafast and slow metabolizers will be excluded from further analysis. A commercial set of "High Pure PCR Template Preparation Kit" according to the manufacturer's instructions (Roche Life Science) will be used to isolate the genomic DNA of the subjects. DNA isolation will be performed from whole blood samples with the anticoagulant EDTA. The protocol consists of lysis of blood cells using lysis buffer, degradation of protein by proteinase K, separation of DNA molecules from the mixture, and purification of DNA using glass mesh columns in a series of washing and centrifugation steps. Measurement of the isolated DNA concentration will be performed using a UV / VIS nanospectrophotometer. DNA samples will be stored at -20 oC until the testing procedure. To determine the allelic variants CYP2D6 \* 3 (rs35742686), CYP2D6 \* 4 (rs3892097) and CYP2D6 \* 5 (whole gene deletion), the commercial set LightMix Kit CYP2D6 \* 3 \* 4 \* 5 / \* 5 will be used according to the manufacturer's instructions (TibMolbiol). The method is real-time PCR (real-time polymerase chain reaction). The test is based on the use of a certain type of fluorescently labeled hybridization assays, the so-called "SimpleProbe" that specifically binds to a sequence that includes a targeted change in DNA. Commercial sets "CYP2D6 TaqMan Copy Number Assay" and "TaqMan Copy Number Reference Assay" according to the manufacturer's instructions (Applied Biosystems) will be used to determine duplication / amplification and the number of copies of the CYP2D6 gene (CYP2D6 \* 1xN). The method is real-time PCR, and the assay is based on the use of fluorescently labeled specific TaqMan probes that bind to the target gene sequence and reference TaqMan probes that bind to a reference sequence that is known to be present in the diploid genome. Relative quantification of the number of copies of the CYP2D6 gene will be possible by analyzing the results using CopyCaller (Applied Biosystems).

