After induction under general anaesthesia, in addition to standard laboratory findings, plasma concentrations of albumin, cholinesterase, gamma-glutamyltransferase, bilirubin, C-reactive protein, procalcitonin will be measured, and pH, pO2, pCO2 and lactate values will be determined from an arterial blood sample. During the procedure, patients will be anesthetized by the method of general balanced inhalation anaesthesia with sevoflurane. Postoperatively, vital parameters, such as temperature, pressure, pulse and diuresis, will be continuously monitored in the ICU, and postoperative values of arterial blood gases, lactate and routine laboratory findings - complete blood count - will be determined. In the ICU patients will receive a total of 500 mg of tramadol intravenously divided into 5 doses during the first 24 hours of admission to ICU.

Plasma concentrations of tramadol, O-demethyltramadol and N-demethyltramadol will be measured 1, 2 and 4 hours after the first dose, and immediately before the 2nd, 3rd and 5th doses. In total, therefore, there will be 6 measurements within 24 hours. Determination of the concentration of tramadol and ODT and NDT metabolites from patient

plasma samples will be performed by high performance liquid chromatography (HPLC) on a Shimadzu Nexera XR (Shimadzu Corporation, Kyoto, Japan) on a reverse phase chromatographic system with fluorescence detection (excitation wavelength 200 a emission 301 nm). Separation will be performed on an Agilent Zorbax SB-C8 column, 3.5  $\mu$ m, 4.6x150 mm (Agilent Technologies, Santa Clara, CA, USA) using a mobile phase consisting of methanol and 1.5 mM H3PO4 in a ratio of 19:81), pH 2.5.

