The analgesic effect of tramadol will be measured in patients who are conscious on the NRS scale (0 - no pain, 10 - most severe pain) 30 minutes before and 30 minutes after tramadol administration. An NRS value of 3 or less will be considered adequate analgesia, and in case of inadequate analgesia, an additional analgesic will be used - morphine 2 mg. In patients with impaired consciousness, the analgesic effect of tramadol will be examined by the Behavioral Pain Scale (BPS) (3 - no pain, 12 - most severe pain) and the Critical Care Pain Observation Tool (CPOT). A BPS value of 5 or less will be considered adequate analgesia, as well as CPOT values less than 2. Consumption of additional analgesic will be recorded regularly. Nausea, vomiting, and newly developed respiratory depression will be reported within 24 hours. In all patients, they will record the total time of hospitalization in ZIM, hospitalization and the patient's outcome - death or survival until discharge from the hospital.

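### The CYP2D6 exclusion from analysis makes no exception for side effects, so events in any ultrafast or slow metabolizer who is given tramadol would go untabulated

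*Combined protocol and SAP*

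**What the plan says.** Patients and methods states that "all patients included in the study will have a blood sample taken for analysis of the CYP2D6 polymorphism", and in the same sentence that "ultrafast and slow metabolizers will be excluded from further analysis". DNA is kept frozen at -20 °C until it is tested. No date is set for the test or its result.

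The dosing text in that section reads "In the ICU patients will receive a total of 500 mg of tramadol intravenously divided into 5 doses", over the first 24 hours in the ICU, with no genotype condition. On safety it says "Nausea, vomiting, and newly developed respiratory depression will be reported within 24 hours", and names no population. The sentence that expressly covers all patients concerns length of stay and death or survival, not side effects.

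The Statistical analysis plan summarises categorical data as absolute and relative frequencies. It defines no set of all treated patients.

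**The concern.** Removing the metabolic extremes may serve a pharmacokinetic question. It gives no reason to leave out adverse events in people who received the drug.

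The Background itself ties CYP2D6 polymorphism to "large individual and population differences in metabolism, analgesic action, and side effects of tramadol". It adds: "The ODT metabolite of tramadol is an active metabolite that has 200-fold higher affinity for opioid receptors than tramadol itself". CYP2D6 is the enzyme that forms this metabolite. Any dosed patients removed by the rule would therefore come from the two ends of the factor that the protocol links to side effects, and respiratory depression is one of the outcomes concerned. At stake is the completeness of a descriptive safety summary. The study's listed objectives are not affected by this point.

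**Working it through.** The plan states no figure to reproduce. The check is mainly a comparison of texts, followed by an illustration.

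**Step 1: is any outcome exempt from the exclusion?** No. The exclusion sentence has no exception. The side-effect sentence names no population. Length of stay and death or survival are to be recorded in all patients, but recording an outcome does not restore it to an analysis from which the patient has been excluded.

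**Step 2: could ultrafast or slow metabolizers be dosed?** The documents leave this open.
- *In favour of dosing being possible.* The eligibility paragraph removes patients from the study (tramadol allergy, recent tramadol, BMI limits, laparoscopy, CYP2D6-inhibiting drugs), whereas the genotype rule removes them from further analysis. Those genotyped are patients already included. Frozen DNA with no test date permits testing after dosing. Dosing has no genotype condition.
- *Against.* The text runs in the order sampling, exclusion, dosing, which fits screening before the first dose.

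**Step 3: what follows if they are dosed?** Let f be the excluded share of dosed patients, rX their risk of a given side effect, and rK the risk in retained patients.
- All-dosed risk = (1 − f) × rK + f × rX
- Reported risk = rK
- Gap = all-dosed − reported = f × (rX − rK)

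None of f, rX and rK is in the documents. Assume rK = 10% and let rX run from 0% to 20%, symmetric so that no direction is built in.

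| f | All-dosed risk at rX = 0%, 10%, 20% | Gap (percentage points) |
|---|---|---|
| 0% (never dosed) | 10.0%, 10.0%, 10.0% | 0, 0, 0 |
| 5% | 9.5%, 10.0%, 10.5% | −0.5, 0, +0.5 |
| 10% | 9.0%, 10.0%, 11.0% | −1.0, 0, +1.0 |
| 20% | 8.0%, 10.0%, 12.0% | −2.0, 0, +2.0 |

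For example, at f = 10% and rX = 20%: 0.90 × 10% + 0.10 × 20% = 11.0%, against 10% reported.

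With equal risks the percentage is unbiased, but events are still missing from the count: f × rX × 100 = 0.5, 1.0 and 2.0 events per 100 dosed patients at f = 5%, 10% and 20%. The table shows how the gap behaves. It does not estimate its size in this study.

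**The case against.** The strongest reply is that no loss has been shown. It requires that ultrafast or slow metabolizers receive tramadol, and the order of the text suits screening first. This stands, and it is why the point is conditional. A reader might infer that such patients will be dosed and their events discarded. The documents do not support that: frozen storage and the wording of the exclusion are equally compatible with a result before dosing.

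Second, safety is not among the four listed objectives, the last of which is to "examine the analgesic effect of tramadol with respect to systemic inflammation and organic dysfunction". Frequencies in the retained metabolizers would describe that population correctly. This also stands: the gap in the working is an error only if the target is all dosed patients, and the plan never sets that target.

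Third, the commitment to report side effects has no genotype limit and could be read as covering everyone treated. That is a fair reading, but nothing says that it overrides the exclusion. The ambiguity is itself a reason for one clarifying sentence.

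Two further inferences should be resisted. Guardian consent ("Informed consent will be signed by the legal guardian if the patient is unable to do so alone for various reasons") might be taken as a sign that results arrive late, but the sentence says nothing about timing and a guardian can consent before surgery. It might also seem that the reported rates would be too low; the documents give no rates by genotype, so the direction is unknown.

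**Conclusion.** The point holds in conditional form and is minor. As written, the genotype exclusion reaches side effects, and nothing in the documents ensures that the genotype is known before the first dose. If some ultrafast or slow metabolizers are dosed, a literal reading leaves their nausea, vomiting and respiratory depression out of every planned frequency.

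Neither size nor direction can be derived. Under the assumed inputs the gap stays within 2 percentage points either way even at f = 20%, but those inputs are illustrative and the verdict does not rest on them. It rests on the missing exception, the absence of any genotype condition on dosing, and the low cost of repair.

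A reader might also infer that the exclusion is sound for the concentration analyses and faulty only for safety. No such claim is made here: the second objective compares concentrations by CYP2D6 polymorphism, so whether the rule suits those analyses is a separate question.

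**What to change.** Add a sentence after the exclusion rule, for example: *The genotype exclusion does not apply to side effects or death; nausea, vomiting, respiratory depression and death will be reported descriptively for every patient given at least one dose of tramadol, overall and by CYP2D6 group.*

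The cost is one small descriptive table whose ultrafast and slow metabolizer rows will probably be sparse, so it should carry counts and no tests. The 24-hour side-effect recording must also continue in these patients once their genotype is known. If it turns out that none of them is dosed, the sentence does no harm and those rows are simply empty. The change does not alter the concentration or analgesia analyses, and it takes no position on who should enter them.

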### **Patients and methods:**

Patients undergoing major abdominal surgery will be included in the study. A major surgical procedure in the abdomen will be considered all procedures that require a surgical approach by laparotomy, which include resections of parts of the organs of the digestive system. Organic dysfunction will be considered laboratory or clinical signs of decreased renal function measured by diuresis with laboratory increase in serum nitrogen metabolites (increase by  $\geq 30\%$  of normal values), and decrease in liver function measured by increase in liver enzymes (increase by  $\geq 30\%$  of reference values), by a decrease in serum cholinesterase levels ( $\leq 20\%$  of normal), an increase in bilirubin by 30% of normal, or a decrease in synthetic liver function as measured by prolongation of PV to  $\leq 60\%$  of INR. A systemic inflammatory response will involve the perioperative presence of two or more of the following factors: body temperature  $> 38$  oC or  $< 36$  oC, leukocytes  $> 12,000$  or  $< 4,000$  mm^3, pCO2  $< 4.3$  kPa, and pulse  $> 90$  / min. In addition, a perioperative increase in CRP, PCT, and lactate above reference values,

as well as a decrease in serum cholinesterase levels, will be considered a systemic inflammatory response. Patients who have a known allergic reaction to tramadol, and patients who have received tramadol for the past 7 days, patients younger than 18 years, BMI <18 kg / m^2> 40 kg / m^2, and patients who do not sign the informed consent will be excluded from the study. Also excluded from the study will be patients who have had laparoscopic surgery, as well as those on chronic therapy with cimetidine, paroxetine, pimozide, metoclopramide, amiodarone, olanzapine, chlorpromazine, fluphenazine, haloperidol, thioridazine, risoridazine, risoridazine drugs inhibit the activity of CYP2D6 enzyme important in tramadol metabolism.

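### A pCO2 below 4.3 kPa counts toward the inflammation label at any perioperative time, although the first arterial sample described is taken under general anaesthesia

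*Combined protocol and SAP*

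**What the plan says.** All places are in the combined protocol and SAP.

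- **Patients and methods, definition.** "A systemic inflammatory response will involve the perioperative presence of two or more of the following factors": temperature, leukocytes, pCO2 and pulse, the last two given as "pCO 2 $< 4.3$ kPa, and pulse $> 90$ / min". No ventilation status is attached to the pCO2 factor, respiratory rate is not offered as an alternative, and no deciding sample is named. The next sentence adds CRP, PCT, lactate and cholinesterase as signs of the same response, without saying how they combine with the four factors.
- **Patients and methods, sampling.** The first arterial sample described is introduced by "After induction under general anaesthesia, in addition to standard laboratory findings", and there "pCO 2 and lactate values will be determined from an arterial blood sample". During the operation "patients will be anesthetized by the method of general balanced inhalation anaesthesia with sevoflurane". In the ICU, "postoperative values of arterial blood gases, lactate and routine laboratory findings - complete blood count - will be determined", without times or ventilation status.
- **Background.** "Hypothermia or hyperthermia, leucocytosis or leukopenia, tachycardia and tachypnoea, are clinical components of SIRS".
- **Objectives.** Objective 3 relates inflammation to tramadol, ODT and NDT concentrations in the early postoperative period. Objective 4 relates it to analgesia.

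**The concern.** Low pCO2 can stand in for tachypnoea only while the patient's own breathing determines it. Under controlled ventilation it depends largely on the settings. A patient ventilated to a low pCO2 gains a factor without being inflamed, and a patient whose respiratory drive is masked loses one.

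The label is the exposure in Objective 3 and part of the exposure in Objective 4. The Statistical analysis plan offers group comparisons and correlations with no adjustment for ventilation, so nothing later in the analysis repairs a wrong label. Misclassification unrelated to inflammation and to drug concentration would tend to dilute the contrast between groups.

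**Working it through.** **1. Reading the passages together.** The plan states no SIRS rate, sample size or effect size, so there is no figure to reproduce. The check is whether the rule, followed as written, lets a post-induction value count.

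- Window: perioperative. A sample after induction falls inside it.
- Factor: pCO2 below 4.3 kPa, without exception.
- Sample: the first arterial gas described follows induction. In the order of the text it precedes the operation, and it precedes the tramadol given in the ICU.
- Construct: the Background names tachypnoea. The definition carries over temperature, leukocytes and pulse, but represents breathing only through pCO2.

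So the post-induction value may count, and nothing says that a postoperative gas overrides it.

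**2. How far one factor can move the label (illustration only; every rate is assumed).** Take independent factors with temperature 0.20, leukocytes 0.35 and pulse 0.30. Let q be the frequency of low pCO2.

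- P(exactly 1 of the other 3) = 0.20×0.65×0.70 + 0.80×0.35×0.70 + 0.80×0.65×0.30 = 0.091 + 0.196 + 0.156 = 0.443
- P(at least 2 of the other 3) = 0.049 + 0.039 + 0.084 + 0.021 = 0.193
- P(positive by the four-factor rule) = 0.193 + 0.443q

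| q | Share positive | Change from q = 0.10 |
|---|---|---|
| 0 | 19.3% | −4.4 points |
| 0.10 | 23.7% | 0 |
| 0.30 | 32.6% | +8.9 points |
| 0.50 | 41.5% | +17.7 points |

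The label can move down as well as up, depending on what ventilation does to pCO2.

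**3. Other assumed rates.** Give each of the other three factors the same probability b. The rise over the two-of-three rule is q × 3b(1−b)². For b = 0.1, 0.2, 0.3 and 0.4, the term 3b(1−b)² is 0.243, 0.384, 0.441 and 0.432. At q = 0.20 the rise is 4.9 to 8.8 points; at q = 0.50 it is 12.2 to 22.1 points.

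**4. The second route.** Suppose a share r meets the marker criteria, independently of the four factors.

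- If the markers are an alternative route, the changes in step 2 are multiplied by (1−r). The rises of 8.9 and 17.7 points become 4.4 and 8.9 at r = 0.5, 1.8 and 3.5 at r = 0.8, and 0.9 and 1.8 at r = 0.9.
- If the markers are an additional requirement, the multiplier is r.

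Either way the effect on the final label is no larger than in the four-factor rule alone. The documents do not give r.

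**The case against.** The strongest reply is that the post-induction sample is only a baseline. It is drawn alongside albumin, cholinesterase, CRP and PCT, Objective 3 concerns the early postoperative period, and postoperative gases are planned. That may well be the intention, but the text does not say so and the perioperative window admits the sample. The objection also shows that the gap is broader: no deciding sample is named for any factor.

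Three further objections stand and limit the point.

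- **Ventilation is inferred.** General anaesthesia for laparotomy makes controlled ventilation likely, but the documents never mention it, nor how many patients stay ventilated in the ICU. The defect needs only the missing exception, which is plain in the text.
- **Low pCO2 alone does not make a patient positive by the four-factor rule.** A second factor is required, and the marker route may already label many patients.
- **Ventilation as a marker of severity.** A reader might infer that ventilated patients are the sicker ones, so that ventilation passes for inflammation. This cannot apply to a sample that every patient gives under anaesthesia. It could apply to the postoperative gases, but the documents hold no ventilation data with which to support it.

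**Conclusion.** The concern holds as a defect in the rule. As written, a pCO2 that probably reflects the anaesthetist's ventilation can help to label a patient as having a systemic inflammatory response for Objectives 3 and 4. The error can go either way.

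Its size is unknown. A reader might infer from the illustration that some 9 to 18 patients per 100 would be wrongly labelled. The documents do not support that: the figure rests wholly on assumed, independent rates, takes low pCO2 as rising from 10% to 30–50%, and covers the four-factor route alone. It shows that a single factor can matter, not how much it does here. The 4.3 kPa threshold itself is not in dispute.

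**What to change.** - State in the definition that the post-induction pCO2 does not count toward the label, and that this factor is taken only from the postoperative blood gases.
- Record ventilation status with each blood gas.
- Repeat the Objective 3 and 4 comparisons with the pCO2 factor dropped for every patient, requiring two of the remaining three factors.

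Dropping pCO2 only for ventilated patients would be a worse remedy. They would need two of three factors while others need two of four. On the rates in step 2, with low pCO2 at 10%, that gives 19.3% against 23.7% positive at equal inflammation, so the label would depend on ventilation by construction. The analysis without pCO2 for anyone applies one rule to all.

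The cost is a sentence in the definition, one data field and one extra analysis. Slightly fewer patients may meet the label.

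### Adequate analgesia is a fixed score cut-off that ignores the recorded pre-dose score, so low pre-dose pain from any cause dilutes, and can bias, the Objective 4 comparison

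*Combined protocol and SAP*

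**What the plan says.** Objective 4 is to "examine the analgesic effect of tramadol with respect to systemic inflammation and organic dysfunction". Under Patients and methods, the analgesic effect in conscious patients is measured on the NRS "30 minutes before and 30 minutes after tramadol administration", so a pre-dose score is available. The rule for reading the scores is absolute: "An NRS value of 3 or less will be considered adequate analgesia". The same sentence links inadequate analgesia to an additional analgesic. For patients with impaired consciousness the rule is again absolute: "A BPS value of 5 or less will be considered adequate analgesia, as well as CPOT values less than 2". The text does not say which of the two scores the cut-off applies to, or whether the before-and-after timing also holds for BPS and CPOT.

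Patients are to receive "500 mg of tramadol intravenously divided into 5 doses during the first 24 hours of admission to ICU". No pre-dose pain score is required for a dose to be given.

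The Statistical analysis plan lists chi-square or Fisher tests for categories; t test, Mann-Whitney, ANOVA or Kruskal-Wallis for numerical variables; and correlation coefficients. Repeated-measures methods are specified for the plasma concentrations only. No paired, change-from-baseline or baseline-adjusted analysis of pain is described.

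**The concern.** Objective 4 is about the effect of tramadol, whereas a score at or below a cut-off describes the patient's state. The two coincide only if patients were above the cut-off before the dose. Where they were not, the dose is classed as adequate whatever tramadol did.

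Two consequences follow. First, even if low pre-dose pain is equally common in all groups, these patients add the same near-certain result to each group and shrink any real difference. Second, if low pre-dose pain is more common in one group, the comparison partly measures that imbalance. Residual perioperative analgesia is one possible cause. The plan neither quantifies it nor lists intraoperative analgesics among the items to be recorded. The resulting bias can go in either direction.

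**Working it through.** The documents state no sample size, response rate or share of patients with low pre-dose pain, so there is no planned figure to reproduce. Every input below is an assumption, for one dose.

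**Notation.** f = share at or below the cut-off before the dose; s = share of those who stay there; p = share of patients in pain who reach the cut-off after the dose. Apparent adequacy A = s·f + (1 − f)·p.

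**1. Equal shares: dilution.** Assume s = 0.9, p = 0.50 without organ dysfunction and 0.35 with it (true gap 15 points), and f = 0.3 in both groups.
- Without: 0.9 × 0.3 + 0.7 × 0.50 = 0.620
- With: 0.9 × 0.3 + 0.7 × 0.35 = 0.515
- Apparent gap 10.5 points, which is 0.7 × 15.

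**2. Unequal shares: bias either way.** Keep 0.620 in the group without dysfunction and vary f in the other group.
- f = 0.5: 0.9 × 0.5 + 0.5 × 0.35 = 0.625. The gap is −0.5 points, so the true difference disappears.
- f = 0.1: 0.9 × 0.1 + 0.9 × 0.35 = 0.405. The gap is 21.5 points, so the true difference is exaggerated.

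**3. No true difference.** Set s = 1 and p equal in both groups. The spurious difference is (1 − p)(f1 − f0). With f = 0.2 versus 0.4 it is 0.5 × 0.2 = 10 points at p = 0.5 and 0.3 × 0.2 = 6 points at p = 0.7. For a pooled two-proportion test at two-sided 0.05 with n per group, let d be the difference and c = 1.96·√(2·p̄(1 − p̄)/n). The rejection probability is Φ((d − c)/SE) + Φ((−d − c)/SE), where SE is the unpooled standard error.

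| f0 vs f1 | Spurious difference (p = 0.7 to 0.5) | Rejection, 50 per group |
|---|---|---|
| 0.2 vs 0.2 | 0 | 0.05 |
| 0.1 vs 0.2 | 3 to 5 points | 0.06 to 0.08 |
| 0.2 vs 0.4 | 6 to 10 points | 0.11 to 0.18 |
| 0.2 vs 0.5 | 9 to 15 points | 0.20 to 0.36 |

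**4. What dilution costs.** Take step 1, 80% power and two-sided 0.05, with n per group = (1.960 + 0.842)² × [a(1 − a) + b(1 − b)]/(a − b)², where the first factor is about 7.85.
- All patients, 0.620 vs 0.515: 7.85 × 0.4854/0.011025 ≈ 346.
- Patients in pain only, 0.50 vs 0.35: 7.85 × 0.4775/0.0225 ≈ 167, or 167/0.7 ≈ 239 enrolled.

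In this illustration, dropping the uninformative patients still needs fewer enrolled patients.

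**5. All five doses.** If dose 1 behaved as in the f = 0.5 case and doses 2 to 5 as in step 1, the pooled gap would be (4 × 10.5 − 0.5)/5 = 8.3 points. An imbalance confined to dose 1 would therefore not remove the gap over all doses.

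**6. After conditioning on pre-dose pain.** Among patients above the cut-off before the dose, step 1 returns the full 15 points. In step 3 the spurious difference is 0 and rejection returns to 0.05.

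**The case against.** **The cut-off is not named as the Objective 4 endpoint.** It stands in the sentence that triggers additional analgesic, and the NRS could be analysed as a numerical variable, even as a change. This stands as a limit. However, it is the only criterion the plan gives, the plan does not say a change will be analysed, and an unadjusted test of post-dose NRS ignores the pre-dose score as well. As written, the choice stays open until the data are seen.

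**Anaesthetic carry-over is not shown.** A reader might infer that patients are still pain-free from the anaesthetic at dose 1, that this lasts longer with organ dysfunction, and that tramadol therefore looks better in that group. The documents do not support this.
- No time is given for dose 1. Separate samples at 4 hours and before dose 2 imply a first interval of at least about 4 hours. If all four intervals were that long (16 hours), dose 1 could fall up to about 8 hours after admission.
- The anaesthetic is described only as "general balanced inhalation anaesthesia with sevoflurane", and no intraoperative analgesic is named.
- A patient whose consciousness is still impaired would be scored by BPS and CPOT, not the NRS.
- The Background remark on liver function, "resulting in increased concentration and decreased plasma elimination of drugs, which is often very difficult to predict", concerns drugs in general. The Background also says tramadol and its active metabolite accumulate in renal failure, so from dose 2 a low pre-dose score may be genuine tramadol effect.

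**Counting only doses given to patients in pain would bring its own bias.** At doses 2 to 5 it would select those in whom earlier tramadol had failed and mix in the effect of additional morphine. This stands, and the fix avoids it.

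**The illustration uses chosen inputs.** This also stands. The exact cancellation in step 2 is one point in a range.

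**Conclusion.** The concern holds in a limited form. The adequacy rule and the planned tests make no use of a pre-dose score that the trial already collects in conscious patients, so low pre-dose pain from any cause counts as adequate analgesia. Dilution of Objective 4 needs only that some patients are at or below the cut-off before the dose: with 30% in both groups, 30% of the true gap is lost (15 to 10.5 points under the assumed rates). Bias needs more, namely that pre-dose pain differs by inflammation or organ dysfunction. The documents give no figure for this, and its direction is not established. The plan should be changed because the better analysis costs almost nothing, not because a given bias has been demonstrated.

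**What to change.** In the Statistical analysis plan, for Objective 4:

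1. Compare the post-dose score at dose 1 between groups, by inflammation and by organ dysfunction, with the recorded pre-dose score as covariate (ANCOVA, or an ordinal or logistic model).
2. As a supporting analysis, show dose-1 response (at or below the cut-off afterwards) among patients above the cut-off before the dose. It should remain supporting, because some high scores fall by regression to the mean.
3. Report the proportion at or below the cut-off over all doses, alongside additional analgesic use, as pain control and not as tramadol effect.
4. Do not restrict doses 2 to 5 by pre-dose score, since that score already reflects earlier tramadol and additional analgesic.
5. State which of the two scores the cut-off applies to in the analysis, how additional analgesic given between the two dose-1 scores is handled, and whether BPS and CPOT follow the same timing. If they do not, the adjusted model covers conscious patients only.

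The cost is some SAP wording and slightly more analysis, and the supporting dose-1 rate rests on fewer patients. Covariate adjustment reduces confounding by pre-dose pain but does not remove other differences between groups in an observational study.
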